13.5. Health Economics Analysis

An economic evaluation will be undertaken to assess the cost-effectiveness of no treatment versus full dose anticoagulation in patients with ISSPE. The evaluation will take the form of an incremental cost-utility analysis to estimate cost per quality adjusted life year (QALY) over 6 months follow up and a cost-effectiveness analysis to estimate cost per VTE avoided over 12 months using routine data sources. Both analyses will be from a health services perspective.

Data collection: Data will be collected on all related health care resource use, concentrating on VTE and bleeding events and investigation of symptoms. This will concentrate on hospitalisations and bed days related to events, visits to primary and secondary care, diagnostic tests undertaken for symptoms potentially related to VTE and major bleeding, and medication use directly related to anticoagulation. This information will be collected from telephone interviews at 12 and 24 weeks, supplemented by information from trial case report forms and hospital records, with targeted extraction data from NHS digital and medical records providing data from 24 to 52 weeks. Unit costs from standard UK sources, for example NHS Reference costs will be sought for all health care resource use items.

In order to calculate QALYs, the EQ-5D-5L questionnaire will be administered to participants at baseline, 12 and 24 weeks. The crosswalk value set will be applied to patient responses to obtain utility scores, in line with current NICE recommendations. In the event of a death, a utility value of 0 will be applied from the date of death to 6 months. Information on VTE recurrence (for the cost-effectiveness analysis at 12 months) will be collected during the trial and from NHS Digital records as previously stated.

Analysis: QALYs will be calculated using responses to the EQ-5D-5L, using the area under the curve approach. Unit costs will be applied to all health care resource use items, and mean resource use (for each category of health care usage) and mean total costs will be calculated for all trial participants. As cost data is likely to have a skewed distribution, the nature of the distribution of costs will be explored, and if the data is not normally

distributed, a non-parametric comparison of means (using bootstrapping) will be undertaken. Multiple imputation will be used to impute all missing values for the EQ-5D and total cost estimates for non-responders. A cost-consequence analysis will initially be reported, describing all the important results relating to resource use, costs and consequences. Incremental cost-effectiveness and cost-utility analyses will then be undertaken to estimate the incremental cost per QALY gained (6 months) and cost per VTE avoided (12 months) respectively, with adjustment for baseline covariates. Discounting is not required as the timeframe is not greater than one year. The robustness of the results will be explored using sensitivity analysis. This will explore uncertainties in the trial based data itself, the methods employed to analyse the data and the generalisability of the results to other settings. The base case analysis will be intention to treat, with a per protocol analysis conducted as a sensitivity analysis. Cost-effectiveness acceptability curves will also be produced to reflect the probability the intervention will be cost effective at different cost per QALY willingness to pay thresholds.

As we would like to explore the cost-effectiveness of a pragmatic treatment policy (i.e. without an expert thoracic radiological review), we propose the use of decision analytical modelling using a decision tree with a 12 month time horizon, to consider cost per VTE avoided and cost per QALY. This will consider bleeding and VTE outcomes only, and related deaths. This modelling will allow us to explore the potential impact of this policy where those with biggest clots may be missed (and are not anticoagulated) and those without SSPE are treated unnecessarily with anticoagulation. A modelling framework has the flexibility in allowing the exploration of a range of assumptions, best and worst-case analysis and threshold analysis.

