3. TRIAL DESIGN AND SETTING

3.1.Trial Design

STOP-APE is an investigator led, multicentre, prospective, randomised controlled, open-label, pragmatic clinical trial with central, blinded, independent adjudication committee (CIAC) endpoint assessment over 3 months for efficacy of withholding anticoagulation for ISSPE. The trial is designed to test the superiority for bleeding events and non-inferiority for recurrent VTE.

Participants will be randomised to either the control arm: full dose anticoagulant treatment as standard care, or the intervention arm: withholding anticoagulation. The choice of anticoagulant will be determined by the responsible treating clinician as part of the standard of care. Pre-randomisation empirical anticoagulation treatment will be allowed for up to 7 days immediately prior to randomisation.

The joint (multiple) primary outcomes of recurrent VTE and clinically relevant bleeding will be established from the trial site clinical notes and electronic health records, patient trial follow-ups and centralised data from hospital episode statistics (HES). The local research team will conduct a safety telephone follow up at 4 weeks, with a permitted window of 1 week either side. Trial follow-ups at 12 and 24 weeks will be performed by the local research team via telephone to complete case report forms and questionnaires. A window of \pm 2 weeks will be permitted for follow-ups.

A 12-month internal pilot will assess feasibility and acceptability with safety of randomisation based on acute reporting radiologists' diagnoses, assessed as part of a nested CTPA study. Note: The nested CTPA study will not stop after the 12-month internal pilot phase and so will be conducted for the full duration of the trial.

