8.3. Study procedures

The following assessments should be performed at baseline:

- Ethnicity
- Concomitant medications
- Smoking status
- Risk factors for bleeding as defined by ISTH
- VTE symptoms include pleuritic pain, breathlessness, chest pain not pleuritic, syncope, haemoptysis, leg pain (unilateral/bilateral), leg swelling or oedema (unilateral/bilateral)
- VTE recurrence risk factors as defined by ACCP
- Height and weight
- Routine blood tests to include Hb, platelet count, creatinine, eGFR, BNP, NT-proBNP, Troponin T, D dimer
- Modified MRC dyspnoea score
- EQ-5D-5L questionnaire to be completed on paper by patient (only required for patients who will be randomised)

At point of randomisation:

• Provide patient with patient card

The following assessments should be performed at 4 week follow up via telephone call with the patient (a window of one week is permitted) and review of the medical record:

- SAE check
- Survival check
- VTE recurrence
- Anti-coagulation medication check to include cessation of treatment, commencement of treatment and change to type of treatment

The following assessments should be performed at 12 week and 24 week follow up via telephone call with the patient (a window of two weeks is permitted) and review of the medical record:

- SAE check
- Survival check
- VTE recurrence
- Bleeding events major bleeding and clinically relevant non major bleeding
- Anti-coagulation medication check to include cessation of treatment, commencement of treatment and change to type of treatment
- Modified MRC dyspnoea score
- EQ-5D-5L questionnaire
- NHS usage for VTE recurrence and associated symptoms/bleeding events- to include primary care visits, emergency department/ambulatory care/AMU visits, hospitalisations and diagnostic investigations for VTE.

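### Section 13.5 imputes the total cost of non-responders, although their hospital use is recorded without the telephone call; recorded components should be kept and only missing ones imputed

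*Protocol*

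**What the plan says.** Protocol section 13.5 sets the missing-data rule for the economic analysis: "Multiple imputation will be used to impute all missing values for the EQ-5D and total cost estimates for non-responders". It does not define a non-responder, and it does not say what happens to the recorded parts of a total that is otherwise incomplete.

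The same section describes two routes to resource use. For the first 24 weeks: "This information will be collected from telephone interviews at 12 and 24 weeks, supplemented by information from trial case report forms and hospital records". After that it continues: "with targeted extraction data from NHS digital and medical records providing data from 24 to 52 weeks". Unit costs are then applied to every item, and mean total costs are formed for all participants. For a death, section 13.5 sets utility to zero from the date of death; it has no matching sentence for cost.

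Other sections confirm that hospital use does not depend on the call. Section 8.3 defines the 12 and 24 week assessments as "follow up via telephone call with the patient (a window of two weeks is permitted) and review of the medical record", covering emergency and ambulatory visits, hospitalisations, VTE investigations and the anticoagulation check. Table 5 in section 10.1 lists the medical record as a second source of health economics data beside the interview. Section 8.5 defines a status in which trial follow-up stops but clinic and central NHS data continue.

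**The concern.** A participant who misses a call lacks the items that only the call can supply, mainly primary care contacts. Admissions, bed days, hospital tests and often anticoagulant use can still be taken from the record. A total that lacks one telephone item is, however, a missing total. If the total is the imputed variable, the recorded parts, which include the most expensive ones, are replaced by a draw from a model. In the 52-week analysis this would also cover weeks 24 to 52, where costs need no response from the participant.

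The cost difference feeds both the cost per QALY and the cost per VTE avoided. Replacing recorded costs adds noise to it. It could also shift it, if people with a bleed or recurrent VTE answer the telephone more or less often than others and the imputation model ignores those events.

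**Working it through.** The protocol gives no figure on this point to reproduce. The check has three parts.

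**1. Which parts of the total need the call**

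- Weeks 0 to 24, hospital use: call, record review (8.3), case report forms and hospital records (13.5, Table 5). Available without the call.
- Weeks 0 to 24, primary care contacts: mainly the call. May be truly missing.
- Weeks 24 to 52: NHS Digital and medical records (13.5). No call needed.

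So for a missed call, only part of the total is missing.

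**2. When whole-total imputation biases the event-cost difference**

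Inputs from section 13.1: bleeding 7% v 3%, and recurrent VTE 2%, taken as equal in both arms. With no overlap the event rates are p = 0.09 (control) and 0.05 (withholding). Assumptions not in the documents: £3,000 per event, and non-response m0 = 10% without an event and m1 with one.

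True difference: (0.09 − 0.05) × £3,000 = £120 per patient.

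If totals are imputed from arm alone, the imputed mean equals the responder mean. The responder event rate is p(1 − m1) / [p(1 − m1) + (1 − p)(1 − m0)].

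Example, m1 = 0.30:
- control 0.063 / (0.063 + 0.819) = 0.0714
- withholding 0.035 / (0.035 + 0.855) = 0.0393
- difference 0.0321 × £3,000 = £96

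| m1 | Estimated difference | Error |
|---|---|---|
| 5% | £126 | +5% |
| 10% | £120 | 0% |
| 20% | £108 | −10% |
| 30% | £96 | −20% |
| 50% | £71 | −41% |

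The percentages are the same at £1,000 and £6,000 per event. If overall non-response is instead held at 10% in each arm, the retained fraction is (1 − m1)/0.9. That is 0.889, 0.778 and 0.667 for m1 = 20%, 30% and 40%, or £107, £93 and £80.

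**3. Simulation of three imputation rules**

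Settings: 733 per arm, 300 runs, 5 hot-deck imputations and the event rates above. Assumed costs: hospital cost averaging £3,000 per event, and other costs averaging £150, plus £150 in the control arm. Hospital cost is assumed fully recorded. Errors are measured against the same trial with complete data, as mean error (SD of error).

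| Rule | m1 = 10% | m1 = 30% |
|---|---|---|
| Whole total, arm only | about £0 (£17) | −£23 (£30) |
| Whole total, recorded event in model | about £0 (£11) | about £0 (£21) |
| Hospital cost kept, rest imputed | about £0 (£2) | about £0 (£2) |

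For scale, at m1 = 10% the SD of the estimated cost difference across simulated trials was £50.5 with complete data. It was £52.1, £51.6 and £50.5 under the three rules. A simple approximation for losing 10% of totals gives an SE ratio of √(1/0.9) = 1.054. At 10% non-response, about 733 × 0.10 = 73 totals per arm would be imputed, including about 5 control and 2 withholding-arm bleeds and 1 to 2 VTEs per arm.

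**The case against.** The best defence is that the sentence speaks of missing values, and nothing says that observed data are dropped. Section 13.5 costs each item, reports each category, and supplements interviews with records. On that reading a non-responder may be someone with no usable resource data at all, such as a participant who has refused all further data collection. The imputation model can also properly be set out in a later analysis plan.

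Much of this stands. A reader might infer that observed costs are certain to be discarded; the protocol does not say so, and the replacement follows only from the clause as worded. What does not stand is that the point is mere detail left for later. Section 13.5 names both the method and the variable imputed, and defers neither. Even if only missing values are imputed, a total without its telephone items is missing.

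A reader might also infer that the cost difference is biased, because people with a bleed or PE miss more calls. No section supports that premise. Section 6.4.3 gives participants a card asking them to contact the team if admitted, and section 9.4 requires SAE reports within 24 hours, so such participants could be easier to trace. If they respond more often, the error changes sign (+5% at m1 = 5%). The 10% in section 13.1 is attrition for sample size, not telephone non-response, and section 13.2.4 expects little missing data. A uniform £3,000 is also crude, since a clinically relevant non-major bleed may involve only a face-to-face evaluation.

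**Conclusion.** The point holds as a matter of wording and method. The protocol fixes imputation at the level of the total, while its own data sources supply the hospital part without the call. Keeping the recorded parts is the better method.

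The dependable loss is precision, and it is modest. With 10% non-response unrelated to events, the error SD is about £17 or £11 against about £2, which widens the SD of the cost difference by about 2% to 3% in the simulation (5% by the simple approximation). Bias is conditional: it needs non-response related to events or their cost, and an imputation model without event status. Section 13.5 neither states nor excludes that model. The illustrated range of +5% to −41% of the event-cost difference shows sensitivity to assumptions and is not an estimate for this trial.

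Two further inferences are not supported. Nothing classes participants who die as non-responders, so the text does not show that their costs would be imputed from survivors; it only lacks a cost rule to match the utility rule. Using NHS Digital cost data only from week 24 is a sourcing choice and not an error, because section 13.5 already names case report forms and hospital records for the earlier period.

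**What to change.** State in section 13.5 that:

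- total cost is built from components;
- recorded hospital components (admissions, bed days, hospital tests, recorded anticoagulant use) are kept as observed for every participant with record access, whether or not the call was answered;
- only missing components, mainly primary care contacts, are multiply imputed, by arm, with recorded hospital cost and adjudicated VTE and bleeding events as predictors;
- for participants who die, recorded costs are used up to the date of death and none after, in line with the utility rule.

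The cost is a few sentences and slightly more programming. No new data collection or participant contact is needed.

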13.6. Qualitative analysis

The interviews will be recorded using a digital recorder from which files will be removed from as soon as possible after interview and stored on a secure computer network until transcribed. Data will be transcribed by a transcription company which has been approved for transcription of medical data. All data and quotes will be anonymised, and each respondent will be allocated a number to ensure that they can be identified if necessary. Digital recordings and corresponding interview transcripts will be stored in an encrypted file on a secure network to which only the primary qualitative researcher will have access. Interview participants will be made aware of this along with their right to withdraw from the interview component up to 7 days following the interview. Data will be managed using NVivo and emerging themes will be identified from the transcripts. A coding framework will be developed to enable analysis of the transcripts and the Framework Method used to summarise the data. Three investigators will separately code a selection of the transcripts to ensure that the codes are triangulated and overall coding will then be carried out by a single researcher.

Analysis will be aimed at understanding whether not treating SSPE is acceptable to patients and clinicians; determining the health seeking behaviours and health utilisation of a no anticoagulation treatment strategy for ISSPE; confirming or challenging existing literature and also at identifying new themes that emerge from the interviews (26). Themes emerging from patient and HCP interviews will be compared both between participants and across the two groups to identify similarities and differences between views in a timely manner to inform the ongoing study (26). A summary of the findings will be sent to the participants.

14. TRIAL ORGANISATIONAL STRUCTURE

14.1.Sponsor

The University of Birmingham is the trial sponsor.

14.2.Coordinating Centre

The trial coordinating centre (Trial Office) is Birmingham Clinical Trials Unit (BCTU) based at UoB. Delegation of tasks to the BCTU, from the Sponsor, are documented in the STOP-APE Clinical Trials Task Delegation Log.

14.3. Trial Management Group

The Trial Management Group (membership detailed in the Administrative Information section) will monitor all aspects of the conduct and progress of the trial, ensure that the protocol is adhered to and take appropriate action to safeguard participants and the quality of the trial itself.

14.4.Trial Steering Committee

A single TSC will be created for the STOP-APE trial and will meet at least annually and as required depending on the needs of the trial office. The TSC will include members who are independent of the investigators, their employing organisations, funders and sponsors. Membership and duties/responsibilities are outlined in the TSC Charter. In summary, the TSC will: provide overall oversight of the trial, including the practical aspects of the study, as well as ensuring that the study is run in a way which is both safe for the participants and provides appropriate feasibility data to the sponsor and investigators. The TSC will consider and act, as appropriate, upon the recommendations of the Data Monitoring Committee (DMC) or equivalent and ultimately carries the responsibility for deciding whether a trial needs to be stopped on grounds of safety or efficacy.

14.5. Data Monitoring Committee

Data analyses will be supplied in confidence to an independent DMC, which will be asked to give advice on whether the accumulated data from the trial, together with the results from other relevant research, justifies the continuing recruitment of further participants. The DMC will operate in accordance with a trial specific charter. The DMC will meet at least annually as agreed by the Committee and documented in the Charter. More frequent meetings may be required for a specific reason (e.g. safety phase) and will be recorded in minutes.

Additional meetings may be called if recruitment is much faster than anticipated and the DMC may, at their discretion, request to meet more frequently or continue to meet following completion of recruitment. An emergency meeting may also be convened if a safety issue is identified. The TSC may consider recommending the discontinuation of the trial if the recruitment rate or data quality are unacceptable or if any issues are identified which may compromise participant safety. The DMC may recommend early stopping of the trial if the interim analyses shows differences between treatments that are deemed to be convincing to the clinical community.

14.6.Central blinded and independent adjudication committee

Data analyses will be supplied in confidence to a central blinded and independent adjudication committee who will assess the end points that inform the primary outcome. The committee will be comprised entirely of independent individuals.

14.7.Finance

The National Institute for Health Research (NIHR) is funding this trial. Clinical Research Network (CRN) support will be sought. Excess cost for the trial remains part of NHS costs while trial resources outside routine care and not covered by the CRN will be funded by the trial in the form of per patient payments to a maximum of £226 per patient.

15. ETHICAL CONSIDERATIONS

The trial will be performed in accordance with the recommendations guiding physicians in biomedical research involving human subjects, adopted by the 18th World Medical Association General Assembly, Helsinki, Finland, 1964, amended by the 48th WMA General Assembly, Somerset West, Republic of South Africa, 1996 (website: http://www.wma.net/en/30publications/10policies/b3/index.html).

The trial will be conducted in accordance with the UK Policy Framework for Health and Social Care, the applicable UK Statutory Instruments, (which include the Data Protection Act 2018) and the Principles of GCP. The protocol will be submitted to and approved by the main REC prior to circulation.

Before any participants are enrolled into the trial, the PI at each site will obtain local R&D approval/assurance. Sites will not be permitted to enrol participants until written confirmation of R&D approval/assurance is received by the BCTU trials team.

It is the responsibility of the PI to ensure that all subsequent amendments gain the necessary local approval. This does not affect the individual clinicians' responsibility to take immediate action if thought necessary to protect the health and interest of individual participants.

16. CONFIDENTIALITY AND DATA PROTECTION

Personal data recorded on all documents will be regarded as strictly confidential and will be handled and stored in accordance with the Data Protection Act 2018.

Participants will always be identified using their unique trial identification number, initials and date of birth on the Case Report Form in correspondence between the Trial Office and site. Participants name and contact number will be collected at the point of registration on the trial registration form in case a central clinical coordinator needs to contact them.

Participants will give explicit consent for this information to be provided to the Trial Office. Participants will give their explicit consent for the movement of their consent forms, giving permission for the Trial Office to be sent a copy. This will be used to perform in-house monitoring of the consent process.

The PI (or delegates) must maintain documents not for submission to the Trial Office (e.g. Participant Identification Logs) in strict confidence. In the case of specific issues and/or queries from the regulatory authorities, it will be necessary to have access to the complete trial records, provided that participant confidentiality is protected.

Interviews will be recorded on an encrypted digital recorder which will be locked in a secured cabinet at the University of Birmingham. Recordings will be transferred onto a secured computer and to a password protected University of Birmingham network folder as soon as possible after each interview. Only the qualitative researchers working on this trial will have access to this folder.

Recordings and transcriptions will be named with a trial-assigned participant number, centre initials, and the date of recording. There will be no participant identifiers in files, databases, or transcripts, which will only be labelled with trial assigned participant numbers. Coding keys matching the name of the participants with their trial participation number will be stored in a password protected spreadsheet, which will be maintained and only accessed by the qualitative researchers. All recordings will be coded and securely transferred to a University of Birmingham approved transcription company or transcriber that has signed the required confidentiality agreements. All transcripts will be anonymised upon receipt. The anonymised interview data (transcripts only) will be uploaded to a 'controlled access' data repository, subject to individual written informed consent from the participants. This has been fully explained in the information sheet, and requires participants to initial a specific statement on the consent form (if they agree).

The Trial Office will maintain the confidentiality of all participant's data and will not disclose information by which participants may be identified to any third party. Representatives of the STOP-APE Trial Office and sponsor may be required to have access to participant's notes for quality assurance purposes but participants should be reassured that their confidentiality will be respected at all times.

